I.b.1. Overview of vitamin D metabolism. Vitamin D is a critical regulator of calcium, phosphorous, and bone homeostasis.⁵²⁻⁵⁵ Humans derive substrate forms of vitamin D (cholecalciferol and ergocalciferol) from cutaneous synthesis and dietary intake. Cholecalciferol and ergocalciferol have little inherent biologic activity and require two hydroxylation steps for full hormonal activity. 25-hydroxylation occurs in the liver and is unregulated and non-rate-limiting. Circulating 25-hydroxyvitamin D [25(OH)D] concentration increases in proportion to UV light exposure and dietary supplement intake, has a half-life of 10-21 days, and is widely accepted as a summary measure of vitamin D intake from cutaneous and dietary sources.⁵⁶⁻⁶² Further hydroxylation to 1,25-dihydroxyvitamin D (calcitriol) occurs predominantly in the kidney and is dependent upon sufficient 25(OH)D availability, particularly among persons with kidney disease.^{28, 63-68} 1,25-dihydroxyvitamin D is a pleiotropic steroid hormone that binds to the vitamin D receptor and regulates gene expression in a diverse array of target tissues.⁶⁹

I.b.2. Vitamin D and the kidney. Traditional effects of 1,25-dihydroxyvitamin D include stimulation of dietary calcium and phosphorous absorption, suppression of parathyroid hormone, and maintenance of bone mineral density. Recently, the potential impact of vitamin D on metabolic and cell regulatory pathways other than those related to traditional mineral homeostasis has attracted increased attention.^{55, 69-71} As one of these potential

[figure not shown]

Figure 3. Survival by estimated GFR (eGFR in mL/min/1.73m²) and urine albumin-creatinine ratio (ACR in mg/g) among 691 Cardiovascular Health Study participants with diabetes, from de Boer et al (ref 34).

pleiotropic actions, 1,25-dihydroxyvitamin D appears to have direct renoprotective effects – this evidence is described below and forms the rationale for Specific Aim 1. It is also possible that calcitriol deficiency due to impaired renal synthesis is a mechanism through which kidney disease leads to CVD and other adverse health outcomes – this latter hypothesis is not the focus of the current application.

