Hypothesis 1c: Beneficial effects of cholecalciferol are strongest among persons who at baseline have low plasma 25-hydroxyvitamin D concentration, albuminuria, and/or impaired GFR.

SPECIFIC AIM 2: To test whether marine omega-3 fatty acids (ω -3 FA, eicosapentaenoic acid plus docosahexaenoic acid, 840 mg per day) prevent the development and progression of DKD, compared with placebo.

Hypothesis 2a: ω -3 FA acids slow progression of albuminuria over 4 years of therapy.

Hypothesis 2b: ω -3 FA reduce loss of GFR over 4 years of therapy.

Hypothesis 2c: Beneficial effects of ω -3 FA are strongest among persons with low baseline levels of plasma eicosapentaenoic acid and docosahexaenoic acid and/or high baseline levels of C-reactive protein.

To test these hypotheses effectively and efficiently, we propose an ancillary study to the Vitamin D and Omega-3 Trial (VITAL). The parent VITAL trial will be a randomized, double-blind, placebo-controlled trial of the benefits and risks of cholecalciferol and ω -3 FA in the primary prevention of cardiovascular disease and cancer. Funded by the NIH (R01 CA138962), 20,000 participants (men ages \geq 60 years, women ages \geq 65 years) will be randomly assigned in a 2x2 factorial design to cholecalciferol 2000 IU daily versus placebo, and to eicosapentaenoic acid plus docosahexaenoic acid 840 mg daily versus placebo. Planned mean follow-up is 5 years. Leveraging the established infrastructure of VITAL, we propose to ascertain effects of cholecalciferol and ω -3 FA on albuminuria and GFR among 1,500 participants with diabetes at baseline. Following the simple and cost-efficient design of the parent VITAL trial, biospecimens will be collected locally and delivered to the VITAL central laboratory by mail. First morning voids will be collected at baseline and year 4 for measurement of urine albumin-creatinine ratio. Blood samples will be collected simultaneously for measurement of GFR (using plasma creatinine and cystatin C), 25-hydroxyvitamin D, eicosapentaenoic acid plus docosahexaenoic acid, C-reactive protein, and hemoglobin A1c.

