III.c. Recruitment of the VITAL Diabetes ancillary study. To conduct the VITAL Diabetes ancillary study outlined in this application, we will identify, recruit, and study a sub-cohort of 1,500 VITAL participants with pre-existing diabetes at baseline. The VITAL Diabetes ancillary study sub-cohort will be recruited during the 3- to 6-month placebo run-in phase of the parent VITAL trial. VITAL will utilize a 3-6 month placebo run-in phase to maximize the proportion of randomized participants who adhere to study medications. Maximizing adherence increases the power of the study, because study outcomes will be analyzed according to treatment assignment (intention to treat).¹³⁷ During the run-in phase, all participants will be asked to take placebo cholecalciferol and placebo ω-3 FA. Participants will receive a follow-up questionnaire reevaluating eligibility criteria and assessing willingness to continue in the trial, pill adherence, and potential adverse effects. Parent VITAL investigators estimate that, of the 40,000 initially willing and eligible individuals enrolled in the run-in, 50% (n=20,000) will be adherent and remain willing and eligible for randomization. The placebo run-in phase provides a critical window of opportunity for ancillary study recruitment.

Persons willing to participate in the parent VITAL trial will return a screening medical history form concurrent with their parent VITAL trial consent form. Those who respond "YES" to the question "Have you EVER been diagnosed as having diabetes?" and who indicate "YES" or "MAYBE" to the question "Are you willing to give a blood sample" (in addition to meeting initial parent VITAL trial eligibility criteria) will be targeted for VITAL Diabetes ancillary study recruitment. With their placebo run-in materials, we will send these persons a DKD ancillary study packet, which includes:

- Letter explaining the rationale for the VITAL DKD ancillary study,
- DKD ancillary study informed consent form,
- DKD ancillary study questionnaire,
- Urine collection kit, and
- Self-addressed, pre-paid FedEx box for returning study materials.

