where β_2 represents the difference in eGFR comparing active vitamin D₃ to placebo, and the corresponding 95% confidence interval and p-value reflect statistical significance of the treatment effect. Parallel equations will be used to test effects of ω -3 FA on changes in albuminuria and eGFR in the absence of interaction with vitamin D₃. An alpha level of 0.05 will be taken to represent statistical significance, without correction for multiple comparisons. We will examine the distributions of change in urine ACR and eGFR and substitute rank-sum comparisons if indicated.¹⁵² We will test differences in proportions of participants attaining the composite dichotomous outcome using the χ^2 test.

Analyses will be performed in accordance with the intent-to-treat principle. For analyses of change in urine ACR and eGFR as continuous variables, only participants who complete study measurements at baseline and year 4 will be included in analyses (complete case analysis). Maximum effort will be made to ensure that all possible participants supply follow-up biospecimens, and all available participants will be included in continuous outcome analyses regardless of adherence to study medications. The relatively large sample size makes it likely that few or no substantial differences in baseline characteristics will be present. In the event that any baseline characteristics are not balanced between treatment groups, however, secondary analyses will add to the ANCOVA model additional terms for such baseline characteristics. If we observe differences by treatment group in medication use (e.g. glucose-lowering or antihypertensive medications) or laboratory covariates (e.g. hemoglobin A1c, CRP) over follow-up, we will explore whether such differences may mediate or obscure effects of study interventions on study outcomes by including additional covariate(s) in the ANCOVA model to assess change in β_2 (treatment effect) toward or away from zero, respectively.

VI.f. *Subgroup analyses.* For the vitamin D intervention, prespecified subgroup analyses will be based on baseline plasma 25(OH)D concentration, baseline urine ACR, baseline eGFR, and race/ethnicity. We hypothesize that beneficial effects of cholecalciferol on urine ACR and eGFR will be greater among

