participants who at baseline (a) have low levels of plasma 25(OH)D, because vitamin D insufficiency may be particularly detrimental below a threshold vitamin D level; (b) have urine ACR ≥ 30 mg/g and/or eGFR < 60 mL/min/m², because persons with DKD may be particularly dependent on adequate 25(OH)D availability for renal synthesis of 1,25dihydroxyvitamin D; and/or (c) are non-Caucasian, i.e. differences in albuminuria and eGFR by race/ethnicity will narrow with vitamin D treatment. For the ω -3 FA intervention, prespecified subgroup analyses will be based on baseline levels of EPA+DHA and CRP. We hypothesize that beneficial effects of ω -3 FA on urine ACR and eGFR will be greater among participants who at baseline have (a) low levels of EPA+DHA, because ω -3 FA insufficiency may be particularly detrimental below a threshold EPA+DHA level; and/or (b) high levels of CRP, because inflammation at baseline will provide opportunity for anti-inflammatory actions of ω -3 FA. Effect modification will be tested by including interaction terms of treatment assignment with subgroup in ANCOVA models (*Equations 3 & 4*).

VI.g. Exploratory adherence and efficacy analyses. All primary analyses will be performed according to the intent-to-treat principle. We plan secondary, *exploratory* analyses for the following limited purposes: (a) to evaluate whether null findings, if observed, are robust (i.e. not readily attributable to defects in the study interventions or their administration); and/or (b) to more comprehensively evaluate the potential range of treatment effects, if treatment effects are observed. We understand and acknowledge that these analyses, which are based on data collected after randomization, may introduce bias into study results. We will therefore use great caution to limit their interpretation. To conduct these efficacy-based explorations, we will first repeat analyses among the subset of participants who report adherence to $\geq 80\%$ of study medications. In addition, we will assess whether changes in 25(OH)D and EPA+DHA levels are associated with changes in urine ACR and eGFR. For the latter analyses, change in 25(OH)D concentrations or change in EPA+DHA concentration (continuous variables) will replace treatment assignment in ANCOVA models.

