where β_3 represents the difference in change in eGFR over time, comparing those on active vitamin D₃ to those on placebo. The corresponding 95% confidence interval and p-value reflect statistical significance of the treatment effect. We will use this model to describe treatment effects at years 2 and 5 but reserve statistical inference for year 5 alone. Corresponding equations will test the effect of omega-3 treatment assignment on eGFR as well as treatment effects on urine ACR, analyzed as a log-transformed continuous variable. The relatively large sample size makes it likely that few or no substantial differences in baseline characteristics will be present. In the event that any baseline characteristics are not balanced between treatment groups, sensitivity analyses will add to the model additional terms for such baseline characteristics. If we observe differences by treatment group in medication use (e.g. glucose-lowering or antihypertensive medications) or

laboratory covariates (e.g. hemoglobin A1c, CRP, IL-6) over follow-up, we will explore whether such differences may mediate or attenuate treatment effects by adding terms for these covariates to the model. We will assess secondary categorical outcomes using discrete Cox proportional hazards models.¹⁸⁴

15f. Subgroup analyses. For the vitamin D intervention, prespecified subgroup analyses will be based on baseline total and bioavailable serum 25(OH)D concentrations, urine ACR, and eGFR as well as race/ethnicity: we hypothesize that effects will be greater among participants who have low 25(OH)D at baseline, who have DKD (urine ACR ≥ 30 mg/g or eGFR < 60 mL/min/m 2) at baseline, or are Caucasian.^{185,186} For the omega-3 fatty acid intervention, prespecified subgroup analyses will be based on baseline levels of EPA+DHA and hsCRP: we hypothesize that effects will be greater among participants who low levels of EPA+DHA or high concentrations of hsCRP at baseline. Effect modification will be tested by including interaction terms of treatment assignment with subgroup in linear mixed models (Equation 2).

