15g. Exploratory adherence and efficacy analyses. All primary analyses will be performed according to the intent-to-treat principle (Section D15e). We plan secondary, *exploratory* analyses for the following limited purposes: (a) to evaluate whether null findings, if observed, are robust (i.e. not readily attributable to defects in the study interventions or their administration); and/or (b) to more comprehensively evaluate the potential range of treatment effects, if treatment effects are observed. We understand and acknowledge that these analyses, which are based on data collected after randomization, may introduce bias into study results. We will therefore use caution to limit their interpretation. We will first repeat analyses among the subset of participants who report continuous adherence to $\geq 80\%$ of study medications. In addition, we will assess whether changes in 25(OH)D and EPA+DHA levels are associated with changes in urine ACR and eGFR. For the latter analyses, change in 25(OH)D concentrations or change in EPA+DHA concentration (continuous variables) will replace treatment assignment in linear mixed models.

D16. Power. We calculated power using simulation (2000 replications) and the following assumptions: independent and equal allocation of participants to each treatment; 1,058 participants (80%) contributing at least one follow-up blood sample (as supported in Section D10); variation in eGFR and its change over time as observed in the preliminary data from our study population (Section D12); and no interaction between treatments. With these assumptions, we have 80% power (two-sided alpha=0.05) to detect a 2.3 mL/min/1.73m 2 difference in eGFR at year 5, comparing each active treatment to placebo. Power for alternative effect sizes is shown in Figure 7. We do not present power for secondary outcomes because the incidence of these outcomes is difficult to predict with available data.

[figure not shown]

Figure 7. Study power by effect size for the primary outcome (difference in estimated GFR in mL/min/1.73m 2).

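### The 25(OH)D subgroup analysis (15f) and the 25(OH)D change analysis (15g) use raw values with no term for season or draw date, so seasonal noise can weaken the treatment-by-25(OH)D interaction and, less strongly, the change association.

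*Combined protocol and SAP*

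**What the plan says.** On the marker, section I.b.1 states that 25(OH)D "concentration increases in proportion to UV light exposure and dietary supplement intake, has a half-life of 10-21 days".

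On the subgroup, Hypothesis 1c (section II) is that "Beneficial effects of cholecalciferol are strongest among persons who at baseline have low plasma 25-hydroxyvitamin D concentration". The 2016 addendum, 15f, says that "prespecified subgroup analyses will be based on baseline total and bioavailable serum 25(OH)D concentrations". It expects larger effects in participants who are low at baseline and says that "Effect modification will be tested by including interaction terms of treatment assignment with subgroup in linear mixed models", pointing to Equation 2. That equation contains treatment, time, their product and a random intercept. The original plan (VI.f) was similar: "prespecified subgroup analyses will be based on baseline plasma 25(OH)D concentration, baseline urine ACR, baseline eGFR, and race/ethnicity".

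On the change analysis, addendum 15g says that "change in 25(OH)D concentrations or change in EPA+DHA concentration (continuous variables) will replace treatment assignment in linear mixed models". The original VI.g has the same plan with ANCOVA. Both label it exploratory and warn in general terms of bias from post-randomisation data.

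On timing, the sub-cohort "will be recruited during the 3- to 6-month placebo run-in phase of the parent VITAL trial" (III.c), and baseline blood is returned at some point in that run-in (IV.a). Follow-up is counted in whole years: year 4 in the original plan (V.d), years 2 and 5 in the addendum (15a). No section supplied uses season, month or date of draw as a covariate, a standardisation or a scheduling rule.

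**The concern.** By the protocol's own account, a single 25(OH)D value reflects UV exposure over recent weeks. Recruitment is by a national mailing and most participants arrange their own blood draw, so baseline samples can fall in any month. Two people with the same year-round level can then be placed differently in 15f because one was drawn in late winter and the other in late summer.

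If vitamin D status over the treatment period is what modifies the effect, season is noise in the modifier, and noise in a modifier shrinks the interaction. In 15g, if the two draws fall at different points of the year, the change score includes a seasonal part unrelated to treatment.

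Both errors lean towards finding no effect modification or no association with achieved level. That matters because 15g is meant partly to show whether a null result is robust, and the subgroup test has limited sensitivity to begin with.

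**Working it through.** **1. What one sample reflects.** Assuming first-order decay, the share of a past contribution left after 90 days is 0.5^(90/21) = 5% at the long half-life and 0.5^(90/10) = 0.2% at the short one. A value drawn in one season says little about sun exposure a season earlier.

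**2. Benchmark for the interaction.** The plan states no power for 15f or 15g, so there is no figure of its own to reproduce here. Its general power method does reproduce. For VI.h, the residual SD is 25 × √(1 − 0.834²) = 13.79. With 600 per arm and a difference of 2.6, z = 2.6/(13.79 × √(2/600)) − 1.96 = 1.30, so power is 90%, as stated. D16 gives 80% power at 2.3 mL/min/1.73m² with 1,058 participants (529 per arm). Its SD is not in the documents; the figures imply (2.3/2.80)/√(2/529) = 13.35. A median-split interaction has four cells of 264.5, so the difference detectable with 80% power is 2.80 × 13.35 × √(4/264.5) = 4.6, twice the main-effect figure.

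**3. Attenuation if 25(OH)D is split.** All inputs are assumptions: annual mean level ~ N(28, SD), other within-person noise SD 3, season A × cos(phase) with uniform draw dates, half-amplitude A of 2-5 ng/mL. Retained fraction = P(truly low | classed low) − P(truly low | classed not low), where truly low refers to the annual mean. Seasonal cost = 1 − retained(raw)/retained(season removed). By simulation:

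| SD | Cut | Retained, season removed | Retained raw, A = 2 / A = 5 | Seasonal cost |
|---|---|---|---|---|
| 8 | 20 ng/mL | 0.714 | 0.684 / 0.564 | 4% / 21% |
| 8 | median | 0.771 | 0.749 / 0.652 | 3% / 15% |
| 10 | 20 ng/mL | 0.785 | 0.763 / 0.665 | 3% / 15% |
| 10 | median | 0.814 | 0.795 / 0.713 | 2% / 12% |
| 5 | 20 ng/mL | 0.447 | 0.406 / 0.268 | 9% / 40% |

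At SD 8 and a cut of 20, misclassification is 7.2% with season removed and 8.0-11.5% without. Most of the loss is therefore ordinary within-person noise, and season adds to it. The only SD of 25(OH)D in the documents is 5 ng/mL, from a type 1 diabetes study (I.b.5), not this population.

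**4. In power terms.** Take an interaction that would have 80% power with season removed. With relative retention f, power is roughly Φ(2.80f − 1.96): 78% at f = 0.98, 60% at f = 0.79, and 39% at f = 0.60 (the SD 5 extreme).

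**5. If 25(OH)D is kept continuous.** Ignoring the other noise, reliability is SD²/(SD² + A²/2). At SD 8 and A = 5 it is 64/76.5 = 0.84; at SD 10 and A = 2 it is 100/102 = 0.98. Power Φ(2.80 × √reliability − 1.96) is then 73% and 79% in place of 80%.

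**6. Change analysis.** For draws d months apart in the calendar, the largest seasonal difference is 2A × sin(πd/12) and its variance over random phase is half the square. The treatment contrast of 16 ng/mL (V.e.1) has pooled variance (16/2)² = 64. Assume an SD of true individual change, s, of 5-8 ng/mL. Reliability is (64 + s²)/(64 + s² + season) pooled, and s²/(s² + season) within arm. For A of 2-5:

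| Offset | Pooled | Within arm |
|---|---|---|
| same month | 1.00 | 1.00 |
| 1 month | 0.96-1.00 | 0.88-0.99 |
| 3 months | 0.78-0.97 | 0.50-0.94 |

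Example: s = 5, A = 5, d = 1 gives a swing of 2.59, variance 3.35 and pooled reliability 89/92.35 = 0.96.

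**The case against.** The strongest objection is that the plan tests what its hypothesis says. Hypothesis 1c concerns low concentration at baseline, VI.f justifies it by a threshold level, and I.b.1 goes on to call 25(OH)D an accepted summary of intake from skin and diet. A reader might infer that 1c concerns lasting deficiency and that the raw value is therefore wrong; the documents do not say so. This stands, and it is why the raw analysis should be kept and not replaced.

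Second, 15f gives no cut-point and does not say whether 25(OH)D is split at all. The 20 ng/mL and median cuts above are illustrations. Every input to the subgroup size is assumed, and the answer runs from negligible to material. This also stands.

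Third, a reader might set a seasonal swing of up to 10 ng/mL (A = 5, six months apart) beside the 16 ng/mL treatment separation and conclude that 15g is badly contaminated. That is one person's worst case against a group mean, it needs the longest run-in (VII.b describes three months), and whole-year visits roughly match the season. The change limb is the weaker one. It does not vanish, because baseline blood can precede randomisation by months and no rule matches the draws.

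Fourth, the addendum is an excerpt that cites sections D10 and D12, which are not in the file. Absence of a season term can be confirmed only for what is supplied.

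**Conclusion.** The point holds as a loss of sensitivity in one subgroup analysis and one exploratory analysis. The protocol itself supplies the reason to expect seasonal variation, and nothing supplied removes it. With half-amplitude 2-5 ng/mL and SD 8-10 ng/mL, season costs about 2-21% of the treatment-by-25(OH)D interaction, depending on the cut-point. The cost reaches about 40% only at SD 5 with the largest amplitude and a cut of 20. It is smaller if 25(OH)D is modelled as continuous. The change association loses little when the draws are within about a month of each other in the calendar, and more if they drift three months apart, chiefly within arm.

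A reader might infer that the main results are biased. They are not: randomisation balances draw season across arms, so the primary treatment effects and the type I error of the interaction test are unaffected. This is a cheap improvement worth making, not a flaw in the primary analysis.

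**What to change.** In 15f, prespecify an analysis on season-standardised baseline 25(OH)D, total and bioavailable: regress the value on sine and cosine of day of year of the draw in all baseline samples, then take the residual plus the overall mean. Report it beside the raw-concentration analysis and state in advance whether each enters as continuous or split, and where. In 15g, add sine-cosine terms for the date of each sample wherever 25(OH)D or its change is the exposure.

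The cost is a paragraph of wording and a few lines of code, with no new samples and no loss of participants. There are four drawbacks:

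- Two versions of the subgroup result must be reported.
- A standardised value is harder to relate to a fixed clinical threshold.
- One seasonal curve removes season only partly in a nationwide cohort in which skin synthesis differs by race/ethnicity (I.b.7), so the gain will fall short of the season-removed figures above.
- V.d mentions only the clock time of the draw and of the last meal, so draw dates, or laboratory receipt dates as a proxy, must be confirmed as available.
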